5.5 Study Evaluations

RCT participants will be asked to complete three brief surveys over a 6-month period. A small sub-set of participants will additionally be invited to participate in qualitative interviews.

Index Unmet Need Screen (survey #1): We will assess unmet needs among trial participants based on the index screen (administered prior to randomization). See **Appendix I** for the Index Unmet Need Survey.

Eight-Week Follow-Up Survey (survey #2): Eight weeks after the index screen, the RA will conduct phone follow-up with each Veteran to assess if they connected to any new resources in the intervening time and if so, to which one(s). See **Appendix J** for the Eight-Week Follow-Up Survey and accompanying phone script.

6-Month Unmet Need Re-Screen (survey #3): Six months after the index screen and by phone, the RA will re-administer the unmet need survey modified slightly

to exclude questions related to preferences for assistance (see **Appendix K** for the Six-Month Unmet Need Survey and accompanying phone script). We will define unmet need reduction in two ways: 1) one or more of baseline unmet needs no longer identified as an unmet need at the 6-month re-screen; and 2) percentage of baseline needs not reported as unmet needs at 6-month rescreen.

Qualitative Interviews with Veterans: Among study participants, we will purposefully select and recruit 60 Veterans to participate in qualitative interviews. The interviews are designed to understand the conditions that facilitate or impede a Veteran connecting to resources, as well as the conditions under which resources do or do not address a Veteran's needs. The RA at each study site will conduct the interviews. See **Appendix L and M** for the Veteran Interview Guides and accompanying phone scripts).

Qualitative Interviews with Representatives of VA and Community Resources: To understand how VA- and community-based programs experience the intervention, we will interview a purposeful sample of the VA- and community-based programs that trial participants used as a result of the intervention. The RA at each study site will conduct the interviews. See **Appendix N** for the Resource Representative Interview Guide and accompanying phone script.

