Appendix I: Index Unmet Needs Screening Tool

DEMOGRAPHICS

1. Please indicate which of following types of people currently live with you in your household (*check all that apply*)

- My spouse or partner
- My child(ren) under age 18
- My adult child(ren) age 18 or older
- My parent(s)
- Extended family
- Roommate(s) not related to me
- Other individuals

2. Overall, which one of the following best describes how well you are managing financially these days?

- Living comfortably
- Doing OK
- Just getting by
- Finding it difficult to get by

3. Are you of Hispanic or Latino origin or descent?

- Yes, Hispanic or Latino
- No, not Hispanic or Latino

4. What is your race? Please select all that apply.

- White
- Black or African-American
- Asian
- Native Hawaiian or other Pacific Islander
- American Indian or Alaska Native
- Other

5. What is your gender

- Man
- Woman
- Transgender man
- Transgender woman
- Non-binary
- Other

HOUSING AND UTILITIES

6. In the past 6 months, have you been living in stable housing that you own, rent, or stay in as part of a household?

- Yes
- No

7. Are you worried or concerned that in the next 2 months you may NOT have stable housing that you own, rent, or stay in as part of a household?

- Yes
- No

7a. (If Yes to Q6 or Q7): Are you already receiving assistance with your housing needs?

7b. (If Yes to 7a): Would you like additional assistance?

7c. (If No to 7a): Would you like assistance with your housing needs?

8. In the past 6 months has the electric, gas, oil or water company threatened to shut off service in your home?

- Yes
- No
- Already shut off
- Not applicable

8a. (If Yes/Already shut off): Are you already receiving assistance with your gas, oil or water company needs?

8b. (If Yes to 8a): Would you like additional assistance?

8c. (If No to 8a): Would you like assistance with your gas, oil or water company needs?

EMPLOYMENT AND FOOD

9. Are you currently:

- Employed for wages
- Self-employed
- Out of work for 1 year or more
- Out of work for less than 1 year
- A Homemaker
- A Student
- Retired
- Unable to work

9a. Do you want help finding or keeping work or a job (check all that apply)?

- Yes, help finding a job
- Yes, help keeping work
- I do not want or need help
- I am already receiving assistance with my employment needs

10. How often were the following statements true for you in the past 6 months?

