i. Within the past 6 months, you worried that your food would run out before you got money to buy more.

- Often true
- Sometimes true

- Never true

ii. Within the past 6 months, the food you bought just didn't last and you didn't have money to get more.

- Often true
- Sometimes true
- Never true

10a. (If Often/Sometimes true to 10i or 10ii): Are you already receiving assistance with your food needs?

10b. (If Yes to 10a): Would you like additional assistance?

10c. (If No to 10a): Would you like assistance with your food needs?

LEGAL AND TRANSPORTATION

11. Are you currently dealing with any legal issues, for which you may need assistance?

- Yes
- No

11a. (If Yes): Are you already receiving assistance with your legal needs?

11b. (If Yes to 11a): Would you like additional assistance?

11c. (If No to 11a): Would you like assistance with your legal needs?

12. In the past 6 months, has lack of transportation kept you from medical appointments, meetings, work, or getting things needed for daily living: *Check all that apply*

- Yes, it has kept me from medical appointments or from getting my medications
- Yes, it has kept me from non-medical meetings, appointments, or getting the things that I need
- No

12a. (If Yes): Are you already receiving assistance with your transportation needs?

12b. (If Yes to 12a): Would you like additional assistance?

12c. (If No to 12a): Would you like assistance with your transportation needs?

SOCIAL AND EMOTIONAL STATUS

13. In the last 6 months, how often did you feel lonely or isolated?

- Never
- Rarely
- Sometimes
- Often

- Always

13a. (If Sometimes/Often/Always): Are you already receiving assistance with your feelings of loneliness or isolation?

13b. (If Yes to 13a): Would you like additional assistance?

13c. (If No to 13a): Would you like assistance with your feelings of loneliness or isolation?

14. Stress is when someone feels tense, nervous, anxious, or can't sleep at night because their mind is troubled. In the last 6 months, how often did you feel stressed?

- Not at all
- A little bit
- Somewhat
- Quite a bit
- Very much

14a. (If Somewhat/Quite a bit/Very much): Are you already receiving assistance with your feelings of stress?

14b. (If Yes to 14a): Would you like additional assistance?

14c. (If No to 14a): Would you like assistance with your feelings of stress?

EXPOSURE TO VIOLENCE

15. Is anyone in your life hurting or threatening you?

- Yes
- No

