15a. (If Sometimes/Often/Always): Are you already receiving assistance with your being hurt or threatened?

15b. (If Yes to 15a): Would you like additional assistance?

15c. (If No to 15a): Would you like assistance with your being hurt or threatened?

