2. Now let's talk about your experience participating in our study. As part of the study, you completed a questionnaire over the phone about your unmet needs (like whether you had reliable transportation) and whether you wanted assistance with the needs you have.
 - a. How did you experience that?
 - b. What did you like and not like?
 - c. What suggestions do you have about how VA could best learn about the resource needs that Veterans have?
3. In the questionnaire you indicated that you had the following needs [insert domain(s)]. I'd like to ask you a few questions about this/these need(s). And at any point, it would be helpful if you could make any important distinctions across before the pandemic, during the pandemic and now.
 - a. Tell me about your experience with [insert unmet need domain(s)], how long you have had this/these needs, how much you worry about this/these needs.
4. How did you feel about receiving a list of services and contact information that could help you to address your need(s) for [insert domain(s)]?
 - a. What worked for you about the experience?
 - b. What didn't work for you?
 - c. Are there ways these handouts could have been made more useful for you?
5. SW ARM ONLY How did you feel about a social worker assisting you to connect to services that might help you with your need for [insert domain(s)]?
 - a. What worked for you about the experience?
 - b. What didn't work for you?
 - c. Are there things the social worker could have done to be more helpful for you?
6. Among all the things that you need to manage in your life, how does [insert domain] need fit in?
7. (For respondents who tried but were unable to connect to new services) Through your participation in the study, we understand that you tried to connect with new services from (insert name(s) of program(s)/organization(s) but were unable to. Can you tell us about this experience?

8. *(For respondents who did not try to connect to new services)* Through your participation in the study, we understand that you did not try to connect with new services from (insert name(s) of program(s)/organization(s) Thinking back to when you were provided a list of services that might be able to help you with your needs – and (*if applicable*) contacted by social worker to assist you in accessing services – what were some of the reasons you didn't try to use these services?
9. What would have made it easier to connect with these services?
 - a. *Probe:*
 - b. Location

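### Two of the eight skip rules in the index screen are wrong as printed: 7a opens on stable housing, and 15a opens on answers that Q15 does not offer

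*Combined protocol and SAP*

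**What the plan says.** Appendix I screens each need with one or more items. For every need except employment, it then uses a skip rule to decide who is asked about assistance: already getting help (a), wanting more (b), or wanting any (c). The b and c items depend on the answer to a.

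- **Housing.** Q6 asks "In the past 6 months, have you been living in stable housing that you own, rent, or stay in as part of a household" (Yes/No). Q7 asks "Are you worried or concerned that in the next 2 months you may NOT have stable housing" (Yes/No). The rule for 7a is "If Yes to Q6 or Q7): Are you already receiving assistance with your housing needs".
- **Safety.** Q15 asks "Is anyone in your life hurting or threatening you" and offers Yes or No. The rule for 15a is "If Sometimes/Often/Always): Are you already receiving assistance with your being hurt or threatened". Item 15c follows as "If No to 15a): Would you like assistance with your being hurt or threatened".

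Section 5.5 says the 6-month survey is modified "to exclude questions related to preferences for assistance". The interview guides in Appendices L and M (question 2 in each) remind the Veteran that the questionnaire covered "whether you wanted assistance with the needs you have".

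**The concern.** Q6 and Q7 point in opposite directions: Yes is the favorable answer to Q6 and the unfavorable answer to Q7. A rule that opens on Yes to either one therefore cannot select Veterans with a housing need. The 15a rule uses the same frequency answers as 13a (loneliness), and Q15 has no such answers.

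What is at stake is the information on current and wanted assistance for two of the nine needs. Followed literally, the form never asks a Veteran who reports being hurt or threatened whether they have help or want it. It also collects housing assistance data from some Veterans without a need and misses some who have one. The scheduled surveys do not recover this, because neither Appendix J (8 weeks) nor Appendix K (6 months) contains the items. For a safety need, and for a Veteran who answers No to both Q6 and Q7, the statement in the interview guides would be untrue for that need.

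**Working it through.** No sample size or power figure is involved. The check compares each opening rule in Appendix I with the answers its parent question offers.

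**Housing.** From the item wording, take need = (Q6 No) or (Q7 Yes). The printed rule is (Q6 Yes) or (Q7 Yes).

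| Q6 stable | Q7 worried | Need | 7a asked as printed | Result |
|---|---|---|---|---|
| Yes | Yes | yes | yes | correct |
| Yes | No | no | yes | asked without a need |
| No | Yes | yes | yes | correct |
| No | No | yes | no | skipped with a need |

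Two of four patterns are misrouted, in opposite directions. With the rule (Q6 No) or (Q7 Yes), none of the four is misrouted.

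As a sensitivity check, suppose No to Q6 is not counted as a need, so that need = (Q7 Yes) only. The No/No row then becomes correct and the Yes/No row stays wrong, leaving one of four misrouted. The printed rule is wrong under either definition.

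**All opening rules.** Trigger answers that the parent item actually offers:

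| Rule | Triggers offered / triggers named |
|---|---|
| 8a utilities | 2/2 |
| 10a food | 2/2 |
| 11a legal | 1/1 |
| 12a transportation | 2/2 |
| 13a isolation | 3/3 |
| 14a stress | 3/3 |
| 15a safety | 0/3 |

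Rules 8a to 14a also fire on the answers that indicate a need. Item 9a (employment) has no rule. Adding 7a gives eight rules, of which 7a and 15a are wrong: 2 of 8.

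**Safety follow-ups.** No Q15 answer opens 15a, and 15b and 15c each need an answer to 15a. So 3 of 3 are unreachable, which means they are missing for 100% of Veterans answering Yes to Q15 if the form is followed. With Yes as the trigger, all three become reachable.

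**Number of Veterans.** This cannot be computed, because the documents give no expected answers to Q6, Q7 or Q15. As an illustration only, assume that 80% to 95% of the 1,760 screened are stably housed and that 5% to 20% of those are worried. The number asked 7a without a need would then run from 1,760 × 0.80 × 0.80 = 1,126 to 1,760 × 0.95 × 0.95 = 1,588.

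**The case against.** The strongest reply concerns consequence. No stated analysis uses the assistance items. RCT eligibility (section 5.2) and Resource Sheets (Appendix A) rest on the needs identified, not on whether help is wanted. Every Veteran in the Assistance arm is offered the social worker whatever these answers are. Section 5.6 takes prior social work use from CPRS records. This stands: the loss is of descriptive data, and nothing here reaches the primary outcome.

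Second, the form is read aloud by a research assistant, who may well treat 15a as opening on Yes. The REDCap build is not shown, and only part of the Appendix G phone script is in the text available for review. So the loss is a property of the printed form and not a demonstrated loss of data. This also stands, and it is the reason to check the form in use. If staff improvise, practice may differ among the three sites.

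Third, counting No/No as a need is an inference, since the available text gives no scoring rule and Q6 looks back 6 months. This has limited force. Rule 7a itself uses Q6 as a route to housing needs, and No is the only answer for which that makes sense. Items 8, 10 and 12 use the same 6-month look-back and open on the unfavorable answer.

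Fourth, other sources might fill the gap. The social worker's assessment covers one arm, and Veterans may decline it. CPRS covers only VA social work contact before the intervention. Neither replaces the missing items.

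Last, the interview statement would be wholly untrue only for a Veteran with no other need. That is fair; it is a minor consequence.

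**Conclusion.** The concern holds. Two of the eight opening rules in Appendix I are wrong as printed, and nothing in the available text corrects them. Rule 7a misroutes two of four answer patterns if No to Q6 counts as a housing need, and one of four if it does not. Rule 15a makes all three safety assistance items unreachable.

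The data loss follows only if the printed rules are applied as written. Q6, Q7 and Q15 are still asked of everyone, so prevalence and need status can be scored correctly from the raw answers. Wrong eligibility, Aim 1 prevalence or Resource Sheets would arise only if need flags were taken from the printed triggers or the follow-up answers, and the available text does not say that they are. The error should be fixed because it is certain and cheap to correct, and the scheduled surveys give no second chance to collect the items.

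**What to change.** 1. In Appendix I, make 7a open on No to Q6 or Yes to Q7, and make 15a open on Yes.
2. Check the form the research assistants actually use at the three sites, including any REDCap branching, against the corrected text.
3. Add one sentence on scoring. It should say that housing and safety need flags come from raw Q6, Q7 and Q15 at index and from Q1, Q2 and Q10 of Appendix K at 6 months. Need-positive answers are No to stable housing, Yes to worry, and Yes to being hurt or threatened.
4. If screening was done under the printed rules, report the safety assistance items as not collected. Restrict housing assistance summaries to Veterans with a housing need by raw Q6/Q7, and state that those answering No to both are missing.

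The cost is two wording changes, one check and one sentence. No new item is needed.

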Appendix J: Eight-Week Follow-Up Survey

Phone Contact:

Hello, my name is _____, I'm calling from the (Name of VAMC). I am trying to reach [Name of Veteran].

Not Present: I'll call back another time, thank you. Is there a good time to try calling back?

Voicemail: Hello, my name is [name of research team member], I am calling from the (Name of VAMC). I wanted to speak with [Name of Veteran] about the Resource Needs Study. It's time to complete one of the brief questionnaires that are part of this study, it will only take about 5 minutes to complete. Please contact me at [name]. If you get my voicemail please leave your name, the best number to reach you at, and the most convenient times to reach you. Thank you.

Present: Hello, my names is [name of research team member] and I work at the (Name of VAMC). I wanted to speak with you about the Resource Needs Study you are participating in. It's time to complete one of the brief questionnaires that are part of this study, it will only take about 5 minutes to complete. Do you have a few minutes now?

If No: When is a good time for you to answer some questions about your social circumstances? (*SCHEDULE A TIME AND CONFIRM BEST CONTACT NUMBER*)

If Yes: Great, let's get started.

Screening Survey

1. Since we last talked on [insert index screening date], were you able to connect with any new programs or services for help with [insert needs identified from index screen)?

Yes

No (skip to Q5)

2. Which programs or services did you connect with?

3. Were you able to get the help you wanted from this (these) program(s)?

Yes

No

4. How did you connect with this (these) program(s)?

Probes

phone call

walk in

web-based

e-mail

5. Why were you unable to connect with the [insert specific resources that were provided to respondent at index screen, e.g., food, employment] programs(s)?

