Our primary Aim 2 analysis will compare *connection to new resources* at 8-weeks post-index screen (our primary outcome of interest) across the study arms. HGLM will be used to control for the nesting of patients within sites. In all models, patient-level intercepts and slopes will be treated as random effects. We predict significantly greater connection to new resources in the ASSISTANCE arm

compared to the SCREENING arm, with the AWARENESS arm falling intermediate to these other two study arms.

Adherence, Utilization, and Clinical Outcomes. We will also conduct a series of secondary analyses to examine whether the study arms influence more distal outcomes, including adherence, utilization, and clinical outcomes. Specifically, to assess the impact of our intervention on more distal healthcare outcomes, we will use a difference-in-difference approach to examine whether changes from baseline at 6-months and 12-months post-referral differ across the three arms of our RCT (N=880). A series of HLM/HGLM analyses with patients nested within sites will examine differences in change from baseline across arms for the adherence, utilization, and clinical outcomes. As with the other analyses, all models will treat patient-level intercepts and predictors as random effects. We will have 80% power to detect small-to-medium effects ($f^2=.05$; OR=2.28) across the three arms using 2-tailed significance tests at the $\alpha=.05$ level, even if we assume a conservative ICC value for patients nested within sites of .01. HbA1c is anticipated to be a relevant clinical outcome for only 40% of the sample and we anticipate missing HbA1c test data for 17% of these Veterans in the year following their index screen; thus, for HbA1c, we will have 80% power to detect small-to-medium effects ($f^2=.08$; OR=2.71) across the three arms using 2-tailed significance tests at the $\alpha=.05$ level, even if we assume a conservative ICC value for patients nested within sites of .01.

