In the Assistance arm, we will hire and train social workers (one per site) to support Veterans to connect with resources following a standard operating procedure informed by current VA SW practices. Following the index screen and provision of tailored Resource Sheets, the RA will offer and encourage Veterans in this arm to receive assistance from a SW. Veterans may choose to opt out, but if they assent, the RA will provide the Veteran with the name and phone number of the SW who will contact the Veteran within two business days of the index screen (making up to five attempts to reach the Veteran by phone). During this initial call, the SW will use a standardized bio-psychosocial assessment tool used by VA SW and proven motivational interviewing methods^{20, 21} to uncover details of the Veteran's unmet needs, identify barriers to resolving the unmet needs, and develop an action plan for the Veteran including how to overcome the identified barriers. In addition, following VA SW practice, the SW will call the resource(s) to which the Veteran has been referred to inform them the Veteran will be coming for services. The SW will conduct initial follow-up by phone one week after the interview/action plan development, with planned subsequent phone outreach every two weeks for up to seven weeks. At each call and as needed (i.e., if Veteran has not yet connected to services), the SW will again employ motivational interviewing methods with the goal of re-affirming the action plan or modifying it as needed. The SW will track and record all Veteran encounters in a research data base, including time spent, challenges and best practices identified.

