11. **Among participants randomized to Arm 3 (Assistance):** Thank you for completing Part One of the study. You are eligible for Part Two of the study and have been randomized to Group C. I would like to provide you with some written material about programs and agencies that might be able to help you with the needs you identified. I will mail you this material within the next two business days. If you like, I can also email the material to you right now and we can review it together over the phone. Would you like to do that?

If Yes to email: Great, I can email that to you right now. (CONFIRM/ASK FOR PARTICIPANT'S EMAIL ADDRESS AND SEND ENCRYPTED EMAIL.)

If No: to email: No problem. You can look for a written list of resources in the mail in the next several days. The information will include my phone number in case you have any questions about the information once you receive it.

11a. I would also like offer you the assistance of a Social Worker (SW), who can assist you to connect to programs and agencies that might be able to help with the needs you identified. Would you like to receive this assistance?

If No: I encourage you to accept this assistance because it can be helpful. Are you sure you don't want assistance from a SW who can assist you to connect to services?

If does not want SW assistance: (GO TO #11b)

If wants SW assistance: (GO TO NEXT QUESTION)

If Yes: Terrific. The SW on the study team – his/her name is (insert name) -- will call you within two business days. Let me give you the name and number of the social worker so you have it. Do you have a pen and paper? (WAIT FOR PEN AND PAPER AND THEN PROVIDE NAME AND NUMBER)

11b. In 8 weeks, I will recontact you to ask a few more questions about your needs. Do you have any questions? (RESPOND TO ANY QUESTIONS ASKED) (MENTION GIFT CARD AND VERIFY MAILING ADDRESS)* Thank you for your time.

**(CIRB Note: local sites will explain their payment process, which differs from the prime site.)*

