2. Now let's talk about your experience participating in our study. As part of the study, you completed a questionnaire over the phone about your unmet needs (like whether you had reliable transportation) and whether you wanted assistance with the needs you have. How did you experience that? What did you like and not like about the experience? What suggestions do you have about how the VA could best learn about the resource needs Veterans have?
3. In the questionnaire you indicated that you had the following needs [insert domains(s)]. I'd like to ask you a few questions about this/these need(s). And at any point, It would be helpful if you could make any important distinctions across before the pandemic, during the pandemic and now.
 - a. Tell me about your experience with [insert unmet need domain(s)], how long you have had this/these needs, how much you worry about this/these needs.
4. How did you feel about receiving a list of services and contact information that could help you to address your need(s) for [insert domain(s)]?
 - a. What worked for you about the experience?
 - b. What didn't work for you?
 - c. Are there ways these handouts could have been made more useful for you?
5. SW ARM ONLY How did you feel about a social worker assisting you to connect to services that might help you with your need for [insert domain(s)]?
 - a. What worked for you about the experience?
 - b. What didn't work for you?
 - c. Are there things the social worker could have done to be more helpful for you?
6. Through your participation in the study, we understand that you received new services from [insert name(s) of program(s)/organization(s)].
 - a. Can you tell us a little about that?
 - b. Can you walk us through the steps you took to get these services? Was it easy to connect to these services? Why or why not? *Probes:*
 - i. Location
 - ii. Access to phone and/or internet
 - iii. Perceived ability to navigate social service delivery system
 - iv. Assistance from others
 - c. What did you think about the organization[s] you were told about?
7. How was your experience receiving services?
 - a. How helpful was/were the service(s) in addressing your need(s)?
 - b. Are there things that worked well or did not?
 - c. How could the service(s) better meet your needs?

- d. What else should I know about the services you received?
 - e. How could the VA better address your unmet needs? (probe for what would be most helpful for the respondent).

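### No supplied rule says whether an 8-week answer naming only the study social worker counts as a connection, so the primary outcome could tilt towards Assistance; the person asking also knows the arm.

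*Combined protocol and SAP*

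**What the plan says.** Section 5.6 (Aim 2) compares connection to new resources "at 8-weeks post-index screen (our primary outcome of interest) across the study arms". Sections 5.1 and 5.5 describe the 8-week survey as finding out whether the Veteran connected to anything new and, if so, to what. Appendix J does this with two items. Q1 asks, about the time since the index call, "were you able to connect with any new programs or services for help with" the needs found at that screen (yes or no). Q2 is open: "Which programs or services did you connect with". Neither Appendix J nor Sections 5.5 and 5.6 define a program or service, or say how Q1 and Q2 combine into the scored outcome.

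Appendix A plans a study social worker for the Assistance arm. The first call comes within two business days of the index screen and a follow-up call one week after the action plan, "with planned subsequent phone outreach every two weeks for up to seven weeks". Take-up is voluntary: "Veterans may choose to opt out, but if they assent", the social worker makes contact. Contacts are logged: "The SW will track and record all Veteran encounters in a research data base". The Appendix G script introduces the social worker as someone "who can assist you to connect to programs and agencies that might be able to help with the needs you identified". Section 5.1 (Adequacy of Protection from Risk) also puts each site's research social worker on call if a Veteran in any arm becomes upset during a survey.

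On masking, Appendix A has the research assistant (RA) open the envelope and tell the Veteran the arm. In Section 5.5 the RA makes the 8-week call, and the Appendix G script has the randomising RA say that they will be the one to call back. No masked assessor or outcome adjudication is described.

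**The concern.** An Assistance Veteran who has had several calls from a social worker in the past eight weeks may honestly answer yes to Q1 and name only that social worker in Q2. The index needs include loneliness and stress, for which those calls could reasonably seem a new service in themselves. The Introduction also speaks of Veterans becoming connected to social work in usual VA care. If such answers are scored as connections, delivery of the intervention is counted as its effect, and in essentially one arm.

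The Section 5.6 analysis of marginal effects does not close the gap. It adjusts only for social work not attributable to the study, measured over the 12 months before the intervention.

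At stake are Assistance against Screening, which is the main predicted contrast, and Assistance against Awareness, which bears on whether the social worker adds anything to the Resource Sheet. Awareness against Screening is not touched by this mechanism.

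A second weakness compounds the first. The question is asked by someone who knows the arm and who, in Assistance, has encouraged the Veteran to accept the social worker. The documents give no input from which to size that effect.

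**Working it through.** The documents state no figure on this point. The calculation shows how many social-worker-only answers it would take to matter.

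**Inputs**
- Respondents per arm: 440/3 ≈ 147 (Section 5.6, 50% response at 8 weeks). At the 65% seen in the team's prior study: 0.65 × 880/3 ≈ 191.
- Control rate p0: not given. Section 5.6 cites earlier work with a 15% greater likelihood and an odds ratio of 2.1, which is compatible with three values.
- Share s of otherwise unconnected Assistance respondents who name only the study social worker: not given. Assumed 2%, 5% and 10%.

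**Step 1: control rates**
- 15 percentage points: (p0 + 0.15)(1 − p0) / [p0(0.85 − p0)] = 2.1, so 1.1p0² − 0.935p0 + 0.15 = 0 and p0 = 0.215 or 0.635.
- Ratio of 1.15: 1.15(1 − p0)/(1 − 1.15p0) = 2.1, so p0 = 0.95/1.265 = 0.751.

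**Step 2: observed Assistance rate with no true effect**

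pA = p0 + (1 − p0)s. The expected number of such answers is 147(1 − p0)s.

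**Step 3: false-positive chance, Assistance against Screening**

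Exact enumeration of two binomials, two-sided 5% unpooled z test. Site clustering and covariates are ignored. Each cell gives s = 2% / 5% / 10%.

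| p0 | pA (%) | Odds ratio | Answers among 147 | False positive, n = 147 (%) | n = 191 (%) |
|---|---|---|---|---|---|
| 21.5% | 23.0 / 25.4 / 29.3 | 1.10 / 1.25 / 1.52 | 2.3 / 5.8 / 11.5 | 6.4 / 12.8 / 34.6 | 6.7 / 15.0 / 42.7 |
| 63.5% | 64.3 / 65.4 / 67.2 | 1.03 / 1.08 / 1.17 | 1.1 / 2.7 / 5.4 | 5.3 / 6.4 / 10.4 | 5.3 / 6.7 / 11.8 |
| 75.1% | 75.6 / 76.3 / 77.6 | 1.03 / 1.07 / 1.15 | 0.7 / 1.8 / 3.7 | 5.3 / 5.9 / 8.1 | 5.3 / 6.0 / 9.0 |

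A pooled z test agrees within one point. A three-arm 2-df chi-square at 147 per arm, by simulation, gives 6.1/12.0/34.8, 5.1/6.2/9.5 and 5.1/5.6/7.5.

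**Step 4: how many answers double the error rate**

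Solving for a 10% false-positive chance at n = 147 gives s = 4.0%, 9.6% and 12.6%. That is 147(1 − p0)s = 4.6, 5.2 and 4.6 answers, or 3.1% to 3.5% of the arm. The count is stable across the three control rates although the share is not.

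**Step 5: the reverse asymmetry**

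Suppose the study social worker is excluded but a new VA social worker counts. If 2/5/10% of otherwise unconnected Screening Veterans name only a VA social worker, the arms swap in Step 2 and the n = 147 error rates in the table arise against Assistance. A rule that treats any social-worker-only answer alike in all arms sets the added term to zero in both, and the error returns to about 5%.

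**The case against.** The strongest reply is that the intent is plain. Section 5.1, Appendix A and the Appendix G script all present the social worker as the route to resources, not as a resource. Appendix M asks "How did you feel about a social worker assisting you to connect to services that might help you" separately from its question on new services received. Q1 is tied to the index needs, and Q4's prompts ask how the Veteran reached the program. Veterans may decline the social worker, and one who accepts has the resources called on their behalf, so a Veteran with social-work contact and no other connection may be uncommon. All of this stands, and it limits the likely share. It does not tell a coder what to do with the answer when it comes.

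Three stronger readings are tempting and not supported:
- A reader might infer that Q1 alone is scored. No passage says so, and Sections 5.1 and 5.5 include which resources were reached. What is missing is a statement that Q2 governs.
- A reader might infer that the study social worker reaches Assistance Veterans only. The on-call role in Section 5.1 allows contact in any arm. It is probably rare and unlikely to change the direction, but planned contact is the accurate description.
- A reader might infer that no rule exists. Section 5.1 (Safety and Data Monitoring Plan) says a Data Analysis Plan was submitted for approval. It is not supplied and may contain one.

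It can also be said that the RA's knowledge of the arm follows from the RA delivering the Resource Sheets. That explains why the randomising RA is unmasked, but not why the same person must ask Q1 and Q2.

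**Conclusion.** The point holds as a gap in the definition of the primary outcome. If social-worker-only answers are counted, comparisons involving Assistance are biased in its favour.

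The size is unknown. The calculation assumes both the share and the control rate, takes no true effect, and ignores site clustering. About 5 such answers among 147 Assistance respondents would double the false-positive chance to 10% under every reading of the cited effect. The 35% figure needs both the largest share tried and the lowest control rate. At control rates of 63.5% or 75.1%, shares of 2% to 5% leave the error at about 5% to 6%. The documents therefore do not support a claim that the trial's result will be materially biased. They support fixing the rule before the outcome is scored.

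The unmasked asker is a separate source of possible bias, of unknown size, that a coding rule would not remove. The change is worth making because it concerns the primary outcome and costs very little.

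**What to change.** First check the Data Analysis Plan. If it does not already settle the matter:

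1. **Primary rule.** Score connection from Q2: at least one named program or service for an index need. A team member masked to arm codes the text, in the same way for completed and future calls. In every arm, an answer naming only a social worker, study or VA, does not count.
2. **Sensitivity analyses.** (a) Exclude only the study social worker, using the Appendix A encounter log to resolve unnamed social workers after the masked coding is locked. (b) Count all social-worker-only answers.
3. **Asker.** Where the existing RAs allow, have Q1 and Q2 asked by an RA who did not randomise that Veteran. This is partial, since Veterans still know their arm.

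Cost: items 1 and 2 need a little coder and analyst time and no change to the survey, provided that Q2 answers are recorded in full. Some genuine new VA social-work connections go uncounted in the primary analysis; sensitivity analysis (a) restores them. An answer that names the study social worker reveals the arm for that record, but the rule is then mechanical. Item 3 depends on staffing that the supplied text does not show. All surveys are by phone, so RAs could in principle swap between sites, but this needs cross-site access and may cost some rapport and response.

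The handling of missing 8-week outcomes, including a tipping-point analysis, is a different issue and should be raised separately.
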